7.2.6 Unscheduled Visits for Additional Safety Monitoring

As detailed in Protocol Section 8 on Safety, patients who experience defined adverse events that require additional safety monitoring will be asked to return at defined intervals for additional follow-up and blood test monitoring (if indicated). It is estimated that routine laboratory safety monitoring may be required every 1-2 weeks until the side effect is resolved or until a proper dose of medication is identified.

7.2.7 Long-term Follow-up

On a voluntary basis, as a component of the consent process, participants will be asked whether they are willing (or not) to be contacted on an annual basis for up to 5 years after completing the study protocol at which time they would be asked to provide an update regarding their health status, symptoms related to their scleroderma and to describe any other treatments that they might have received for this condition.

7.3 SUMMARY OF STUDY SCHEDULE AND ASSESSMENTS

Figure 7.3a Study Schedule Flow Diagram

[figure not shown]

Table 7.3a: Table of Study Visits & Assessments

SCREENING AND INITIAL 6 MONTHS

Type of Visit:	Screen	Baseline	Phone	Regular	Phone	Regular	Regular	Regular	Regular	Regular	Regular
Visit #:	S1-2	1	2	3	4	5	6	7	8	9	
Study Month:		0	0.5	1	1.5	2	3	4	5	6	
Assessments											
Medical history	X	X	X	X	X	X	X	X	X	X	
Physical exam	X	X		X		X	X	X	X	X	
Vital signs**	X	X		X		X	X	X	X	X	
Concomitant Medication	X	X	X	X	X	X	X	X	X	X	
Medication Reconciliation	X	X	X	X	X	X	X	X	X	X	
Adverse events			X	X	X	X	X	X	X	X	
Lung function testing	X	X					X				X
Blood Test Monitoring	X			X		X	X	X	X	X	
Questionnaires	UCLA SCTC GIT	X					X				X
HRCT scan of chest	X										
Pregnancy test*	X	X		X		X	X	X	X	X	
Blood for Bio-Repository		X									

* For women who are able to become pregnant; require a blood test at screening then urine testing.

** Only need height at screening.

MONTHS 7 – 19 & EXTRA VISITS

Type of Visit:	Phone	Regular	Phone	One Year	Phone	Regular	Phone	18 Month	Final Phone	Extra
Visit #:	10-11	12	13-14	15	16-17	18	19-20	21	22	
Study Month:	7, 8	9	10, 11	12	13, 14	15	16, 17	18	19	Yrs 2-5
Assessments										
Medical history	X	X	X	X	X	X	X	X	X	X
Physical exam		X		X		X		X		
Vital signs**		X		X		X		X		
Concurrent Medication	X	X	X	X	X	X	X	X	X	X
Medication Reconciliation	X	X	X	X	X	X	X	X		X
Adverse events	X	X	X	X	X	X	X	X	X	X
Lung function testing		X		X		X		X		
Blood test monitoring		X		X		X		X		
Questionnaires		X		X		X		X		
HRCT scan of chest								X		
Pregnancy test*		X		X		X		X		
Blood for BioRepository				X				X		

* For women who are able to become pregnant; require a blood test at screening then urine testing.

** Only need height at screening.

7.4 CONCOMITANT MEDICATIONS & TREATMENTS DURING THE STUDY

All concomitant prescription, over-the-counter and non-prescription medications taken during study participation will be recorded on the case report forms (CRFs) and checked for compatibility with the study drugs as defined in Section 7.5.

7.5 PROHIBITED MEDICATIONS AND TREATMENTS DURING THE STUDY

7.5.1 Prohibited Medications & Treatments with DMARD Activity

Medications from the following list, and their biosimilars, are prohibited and may not be taken prior to screening in amounts (or for time intervals) that exceed allowable limits as detailed in Exclusion Criteria #15 and #16. They may not be taken while participating in the active drug treatment phase of this study (except for MMF and PFD when specifically administered as study drugs according to the study protocol).

Prior use of these medications must be consistent with Exclusion Criteria #15

a) Oral or short half-life drugs with potential DMARD activity

• Anakinra	• Dasatinib	• Nintedanib
• Apremilast	• Imatinib	• Pirfenidone
• Azathioprine	• Leflunomide	• Pomalidomide
• Baricitinib	• Methotrexate	• Rilonacept
• Cyclophosphamide oral	• Mycophenolate mofetil	• Tacrolimus
• Cyclosporine	• Nilotinib	• Tofacitinib

b) Intravenous or injectable drugs with potential DMARD activity

• Abatacept	• Cyclophosphamide IV	• Rituximab
• Adalimumab	• Etanercept	• Sarilumab
• Alemtuzumab	• Guselukumab	• Secukinumab
• Belimumab	• Golimumab	• Tocilizumab
• Canakinumab	• Infliximab	• Ustekinumab
• Certolizumab	• Ixekizumab	

7.5.2 Prohibited Medications & Treatments that may Increase Immune Suppression Risk

a) Prednisone >10mg/day (or equivalent corticosteroid).

NOTE: a brief pulse of prednisone to \leq 30 mg/day that lasts no more than 7 days before returning to a dose of \leq 10 mg is permissible if indicated for a temporary intercurrent medical condition.

a) Live vaccines administered within 30 days of, or after randomization including:

- Bacillus of Calemett and Guerin (BCG) Vaccine
- Measles Virus
- Mumps

- Polio Virus
- Rotavirus
- Rubella
- Small pox
- Typhoid
- Varicella Virus
- Yellow Fever
- Live influenza vaccine

7.5.3 Prohibited Medications that may Interfere with Study Drug Absorption/Metabolism

- a) Antacids containing Magnesium and Aluminum Hydroxides **should not** be taken together (at the same time) with MMF due to their impact on the absorption of MMF.
NOTE: Antacids may be used, but should not be taken within 2 hrs of MMF.
- b) Proton Pump Inhibitors (PPIs) **should not** be taken together (at the same time) with MMF due to their impact on the absorption of MMF.
NOTE: PPIs may be used, but should not be taken within 2 hrs of MMF.
- c) Sevelamer and other calcium free phosphate binders **should not** be taken together (at the same time) with MMF due to their impact on the absorption of MMF.
NOTE: Calcium free phosphate may be used, but should not be taken within 2 hrs of MMF.
- b) Cholestyramine **should not** be taken due to interference with enterohepatic recirculation of MMF
- c) Cyclosprine **should not** be taken due to interference with enterohepatic recirculation of MMF
- d) Norfloxacin and Metronidazole **should not** be taken together as a combination therapy while on therapy with MMF due to interference with serum levels of MMF
- e) Ciprofloxacin and/or Amoxicillin plus Clavulanic Acid may temporarily interfere with the enterohepatic recirculation of MMF producing temporary reductions in serum MMF levels.
NOTE: Temporary use for 2 weeks or less is of unclear significance but sustained use of these antibiotics is not recommended.
- f) Ciprofloxacin and other Fluoroquinolones which are moderate inhibitors of CYP1A2 may interfere with the metabolism of PFD, significantly increasing drug exposure.
NOTE: Use of Ciprofloxacin at a maximal dose of 500 mg twice daily for up to two weeks is allowed.
NOTE: If temporary use for Ciprofloxacin at a dose of 750 mg twice daily (or other fluoroquinolone at high dose) is required for 2 weeks or less, the daily dose of PFD should be reduced by 1 capsule three times a day during the period of concomitant use (patients on 3 capsules should reduce to 2, while patients on 2 capsules should reduce to 1)
- g) Rifampin may temporarily interfere with serum levels of MMF.
NOTE: Temporary use for 2 weeks or less is of unclear significance but sustained use of these antibiotics is not recommended.
- h) Fluvoxamine, enoxacin or other strong CYP1A2 inhibitors **should not** be taken due to their impact on the metabolism of PFD, which can significantly increase drug exposure
- i) Smoking, which is a strong inducer of CYP1A2, is not allowed during the study

7.5.4 Restrictions on Medications with Other Adverse Interactions

- a) Hormonal contraceptives may not be effective during administration of MMF due to interactions with drug metabolism and a second type of contraception must be used to participate in study if one of the following hormonal contraceptive is used:
 - Levongogrelstrel
 - Norethindrone
 - Mestranol
 - Norgestrel
 - Ethinyl estradiol
 - Etonogrelstrel
- b) Use of tanning beds or medical phototherapy that includes UV light exposure are contraindicated during the use of PFD due to their impact on photosensitivity reactions.

7.6 PROPHYLACTIC MEDICATIONS, TREATMENTS, AND PROCEDURES

Prophylactic use of topical sunblock agents: PFD is associated with photosensitivity. In addition to advising patients to wear protective clothing, hats, and avoid extended sun (or tanning light) exposure, they will be advised to use over the counter sunblock as a prophylactic therapy if sun exposure is anticipated.

Prophylactic consumption of PFD with food: Patients are advised to take PFD with food to help decrease gastrointestinal side effects.

8 ASSESSMENT OF SAFETY

8.1 SPECIFICATION OF SAFETY PARAMETERS

Safety parameters will include frequency of events and/or incidence of study subjects experiencing events, by study arm for the following:

- a) Study-defined Treatment failures
- b) Study-defined Treatment emergent AEs of Special Interest
- c) All treatment emergent AEs, total and by organ system classification
- d) All treatment related AEs, total and by organ system classification
- e) All treatment emergent SAEs, total and by organ system classification
- f) All treatment related SAEs, total and by organ system classification
- g) All treatment emergent deaths
- h) All treatment-emergent AEs and SAEs that result in discontinuation of treatment
- i) Time to treatment failure, treatment emergent AEs and SAEs that result in discontinuation of treatment, and death

8.1.1 Definition of Adverse Events (AEs)

Adverse event means any untoward medical occurrence, such as an abnormal laboratory finding, physical sign, symptom, or diagnosis of a disease state, that is temporally associated with the use of an interventional treatment or procedure in a human subject regardless of whether or not it is considered intervention-related [consistent with 21 CFR 312.32 (a)].

8.1.1.1 Treatment-emergent AEs (TEAEs):

TEAEs are those that start or worsen after the start of study treatment and up to 7 days (for AEs) and 30 days (for serious AEs) after the last dose of study treatment. This AE definition would include the following:

- Any pre-existing condition that increases in severity or changes in nature during or as a consequence of the study treatment administration
- Complications resulting from protocol-mandated procedures
- AEs occurring as a result of product withdrawal, abuse or overdose
- A change in a laboratory variable if considered by the investigator to be clinically significant or if it is caused (or should have caused) the investigator to reduce or discontinue the use of the product or initiate a non-protocol therapy or procedure

8.1.1.2 AEs of Special Interest:

AEs of Special Interest represent a specific subset of all AEs and are defined by the study protocol based on two distinct features: 1) their likely association with the investigational drug(s), and 2) the presence of pre-specified study drug management guidelines that are to be followed when the AE occurs.

8.1.2 Definition of Serious Adverse Events (SAEs)

An AE or suspected adverse reaction is considered "serious" if, in the view of either the investigator or sponsor, it results in any of the following outcomes:

- Death,
- A life-threatening AE
- Inpatient hospitalization or prolongation of existing hospitalization
- A persistent or significant incapacity or substantial disruption of the ability to conduct normal life functions
- A congenital anomaly/birth defect.

Important medical events that may not result in death, be life-threatening, or require hospitalization may be considered serious when, based upon appropriate medical judgment, they may jeopardize the patient or subject and may require medical or surgical intervention to prevent one of the outcomes listed in this definition. Examples of such medical events include allergic bronchospasm requiring intensive treatment in an emergency room or at home, blood dyscrasias or convulsions that do not result in inpatient hospitalization, or the development of drug dependency or drug abuse. [Consistent with 21 CFR 312.32 (a)]

8.1.3 Definition of Unanticipated Problems (UP – unexpected AEs & Problems)

An AE or suspected adverse reaction is considered "unanticipated" if it is not listed or characterized in the Package Insert or in the current Investigator Brochure or is not listed at the specificity or severity that has been observed; or, if an investigator brochure is not required or available, is not consistent with the risk information described in the general investigational plan or elsewhere in the current application, as amended. For example, under this definition, hepatic necrosis would be unexpected (by virtue of greater severity) if the investigator brochure referred only to elevated hepatic enzymes or hepatitis. Similarly, cerebral thromboembolism and cerebral vasculitis would be unexpected (by virtue of greater specificity) if the investigator brochure listed only cerebral vascular accidents. "Unexpected," as used in this definition, also refers to AEs or suspected adverse reactions that are mentioned in the investigator brochure as occurring with a class of drugs or as anticipated

from the pharmacological properties of the drug, but are not specifically mentioned as occurring with the particular drug under investigation. [Consistent with 21 CFR 312.32 (a)]

8.2 CLASSIFICATION OF AN ADVERSE EVENT

8.2.1 Severity of Event

The intensity of all AEs will be graded using a five-point grading scale in which the following descriptions of severity will apply. Note that for some AEs, Grades 4 and/or 5 may not be applicable. In those cases only 3 different grades (Grade 1-3) are to be considered:

- 8.2.1.1 **Grade 1:** “Mild”; asymptomatic or mild symptoms; clinical or diagnostic observations only; intervention not indicated.
- 8.2.1.2 **Grade 2:** “Moderate”; minimal, local or noninvasive intervention indicated; limiting age-appropriate instrumental ADL*.
- 8.2.1.3 **Grade 3:** “Severe”; medically significant but not immediately life-threatening; hospitalization or prolongation of hospitalization indicated; disabling; limiting self care ADL**.
- 8.2.1.4 **Grade 4:** “Life-threatening consequences”; urgent intervention indicated.
- 8.2.1.5 **Grade 5:** “Death related to AE”.

*Instrumental ADL refer to preparing meals, shopping for groceries or clothes, using the telephone, managing money, etc.

**Self care ADL refer to bathing, dressing and undressing, feeding self, using the toilet, taking medications, and not bedridden.

8.2.2 Relationship to Study Drug

For all collected AEs, the clinician who examines and evaluates the participant will determine the AE's causality based on temporal relationship and his/her clinical judgment. A binary assessment (related/not related) will be made and take into consideration the natural history of the underlying disease, concurrent illness, concomitant therapy, study-related procedures, accidents, and other external factors. While the relationship to the study drug (related/not related) is part of the documentation process, it is not a factor in determining what is or is not reported in the study. All AEs are recorded regardless of relatedness.

- 8.2.2.1 **Related** The AE is known to occur with the study agent, there is a reasonable possibility that the study agent caused the AE, or there is a temporal relationship between the study agent and event. Reasonable possibility means that there is evidence to suggest a causal relationship between the study agent and the AE. An AE can be deemed related even if other factors may have contributed to the event.
- 8.2.2.2 **Not Related** There is not a reasonable possibility that the administration of the study agent caused the event, there is no temporal relationship between the study agent and event onset, or an alternate etiology has been established or appears to provide a plausible explanation

(e.g. the participant's clinical condition, underlying disease or concomitant treatments).

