Dose Management: Hold study drug until there is a clinically stable resolution of the problem. In addition, if other causes of noted conditions are identified (e.g., medications, dehydration, etc.), they should be treated and stabilized before restarting on study drug. If there is no improvement, the study drug will be stopped and subject withdrawn from study.

f) Ongoing infection whose management would be significantly compromised by continued drug-associated immunosuppression or any hospitalization, surgery or infection requiring antibiotic therapy where the immununosuppressive effects of MMF are determined by the clinical site investigator to likely complicate the patient's response to therapy.

Dose Management: Hold study drug until the potential interaction with the medical condition in question has resolved. Once the patient is stable, the study drug can be restarted without dose modification.

g) Development of a proven malignancy other than basal cell cancer of the skin or cervical carcinoma in situ removed entirely by excisional biopsy or surgical resection.

Dose Management: Study drug will be permanently discontinued and subject withdrawn from study.

h) Any adverse event felt by the investigator to be possibly or probably related to the administration of MMF and of a clinical significance sufficient to warrant holding or discontinuing drug.

Dose Management: Management as follows:

- Hold study drug until there is a clinically stable resolution of the problem. In addition, if other causes of noted conditions are identified, they should be treated and stabilized before restarting on study drug.
- Once a stable recovery occurs, as judged by the clinical site investigator, MMF will be reintroduced at a daily dose of 1000 mg (500 mg twice daily doses) and increased by 500 mg (one 250 mg capsule for each of the twice daily doses) every two weeks. At the discretion of the clinical site investigator, after taking into account whether the study drug was likely or probably related to the adverse event, the final maintenance dose may be either the last regular dose of MMF taken by the patient or one capsule per-dose less (500 mg/day less).
- In the event of repeat toxicity, the same cycle should be repeated except with the intention of achieving a maintenance dose equal to 1000 mg/day less for MMF.

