- Reduce PFD/Plac dose by 1 capsule for each of the three times daily doses and if symptoms do not improve, the study drug should be held until the potential interaction with the medical condition in question has resolved. Once the patient is stable, the study drug can be re-started and titrated according to the original schedule as tolerated.

f) For photosensitivity skin reactions or rash that do not respond to UVA/UVB sunscreen, sun avoidance, and/or the use of over the counter topical corticosteroid creams, and are of sufficient clinical importance to warrant drug dose adjustment.

Management:

- Reduce PFD/Plac dose by 1 capsule for each of the three times daily doses and if symptoms improve/resolve, can increase back to the original dosing after 2 weeks as tolerated. If the higher dose is still not tolerated, then 1 capsule less for each of the three times daily doses can be continued.
- Reduce PFD/Plac dose by 1 capsule for each of the three times daily doses and if symptoms do not improve, the study drug should be held until the potential interaction with the medical condition in question has resolved. Once the patient is stable, the study drug can be re-started and titrated according to the original schedule as tolerated.

g) An infection whose management requires the use for Ciprofloxacin at a dose of 750 mg twice daily (or other fluoroquinolone at high dose) for 2 weeks or less will require a dose adjustment for PFD/Plac.

- During the course of antibiotic treatment, the daily dose of PFD/Plac should be reduced by 1 capsule three times a day during the period of concomitant use

(patients on 3 capsules should reduce to 2, while patients on 2 capsules should reduce to 1).

h) Any adverse event felt by the investigator to be possibly or probably related to the administration of PFD/Plac and of a clinical significance sufficient to warrant adjusting or discontinuing drug.

Dose Management: Management as follows:

- Reduce PFD/Plac dose by 1 capsule for each of the three times daily doses and if symptoms improve/resolve, can increase back to the original dosing after 2 weeks as tolerated. If the higher dose is still not tolerated, then 1 capsule less for each of the three times daily doses can be continued as the maximally tolerated treatment dose.

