  - a. Using 4 points increments: worsen (1 to 4,  $\geq 5$ ), no change (=0), improved ( $\leq -13, -12$  to -9, -8 to -5, -4 to -1).
  - b. Improved (< -5), no change (-5 to 5), and decreased (> 5).
9. The proportion of participants in each treatment arm achieving the TDI focal score at month 18 as :
  - a. Improved by 1-3, 4-6 and 7-9 points, no change (0) and worsened by 1-3, 4-6 and 7-9 points.
  - b. Improved (>0), no change, deterioration (<0).
10. Tolerability and toxicity of combined MMF and Plac vs MMF and PFD over the course of the 18-month treatment period.
  - a. The time from start of treatment to withdrawal or removal from active drug therapy for any reason.
  - b. Number of participants with treatment-emergent adverse events related to study medication as assessed by system organ classification using preferred Medical Dictionary for Regulatory Activities (MedDRA) terms.

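### Timing alone makes an event Related and a plausible other cause alone makes it Not Related, so one treatment-emergent event can meet both definitions and related-event counts depend on the assessor

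*Protocol*

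**What the plan says.** Protocol 8.2.2 asks the examining clinician for a yes/no causality judgement on every adverse event. The lead-in tells the clinician to use timing and clinical judgement and to "take into consideration the natural history of the underlying disease, concurrent illness, concomitant therapy, study-related procedures, accidents, and other external factors". Two definitions follow, each a list of alternatives.

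- *Related*: the event is known to occur with the agent; or there is a reasonable possibility of causation; "or there is a temporal relationship between the study agent and event". The text adds that other contributing factors do not rule this code out.
- *Not Related*: no reasonable possibility; or no temporal relationship; "or an alternate etiology has been established or appears to provide a plausible explanation", with underlying disease and concomitant treatment among the examples.

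SAP 11.5.2 repeats both definitions. Protocol 8.1.1 already describes an adverse event as one "that is temporally associated with the use of an interventional treatment or procedure in a human subject", and defines a treatment-emergent event (TEAE) as one that starts or worsens on treatment or within 7 days of the last dose (30 days if serious).

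The coding feeds SAP secondary endpoint 10b, "Number of participants with treatment-emergent adverse events related to study medication as assessed by system organ classification", and items d and f of the SAP section 11 list (related TEAEs and related serious TEAEs).

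**The concern.** A binary attribution rule should place each event in exactly one category. Here the timing ground does no sorting among the events that can enter endpoint 10b, because being treatment-emergent already implies it. The alternative-cause ground is also easily met in patients with a multisystem disease who take an immunosuppressant.

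Take a pneumonia during influenza season in a patient on study drug. One site codes it Related on timing, another codes it Not Related on alternative cause, and both have followed the text. At stake is a named secondary endpoint that serves the tolerability objective. If assessors lean on timing, the related tables approach the all-TEAE tables. If they differ in which ground they apply, the tables partly reflect coding habits.

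**Working it through.** No design figure depends on this rule, so there is none to reproduce. The check is a comparison of texts, followed by two scale checks and an illustration.

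**1. Does every TEAE meet the timing ground?** A TEAE starts or worsens between first dose and 7 days (30 if serious) after last dose. Section 8.2.2 gives no interval of its own for a temporal relationship; if the TEAE window is taken as that interval, the answer is yes. It is not yes for every adverse event: Protocol 8.3.1 records events from informed consent, and one that began and ended before the first dose has no temporal relationship to the agent.

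**2. Which definitions does each kind of event meet?**

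| Event | Related? | Not Related? |
|---|---|---|
| Before first dose | not by timing | yes (no temporal relationship) |
| TEAE, reasonable possibility of causation, no plausible other cause | yes | no |
| TEAE with a plausible background cause | yes (timing) | yes (alternative cause) |

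The third row is the defect. The remark about contributing factors permits a Related code but does not require it, so it is not a precedence rule.

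**3. Does adjudication settle it?** Under Protocol 8.5.1 a blinded three-member committee makes the final determination, but only for serious events and by reference to the same 8.2.2. Non-serious events have no independent review.

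**4. Scale, earlier pirfenidone trial in SSc-ILD (Protocol Table 2.1.6a).** Not related 5, possibly related 13, related 43; 5 + 13 + 43 = 61 patients with any TEAE, of 63.

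- Related: 43/63 = 68.3%.
- Related or possibly related: 56/63 = 88.9%.
- Timing-only reading: 61/63 = 96.8%.

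The largest possible shift is 61 − 56 = 5 patients if possibly related already counts as related, or 61 − 43 = 18 if it does not.

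**5. Scale, mycophenolate arm of SLS II (Protocol Table 2.3.1.1.4c-2).** The committee judged 3 of 42 serious events treatment-related (7.1%), in 3/69 patients (4.3%). Any serious event occurred in 27/69 (39.1%). A timing-only reading is bounded by 42 of 42 events and 27 of 69 patients, assuming all began on treatment.

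Neither trial used a binary scale (three categories in step 4, four in step 5), so these figures are bounds and not predictions.

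**6. Illustration of dilution.** Assume drug-caused incidence *d* in one organ class of 20% against 40%, and independent background illness coded as related with probability *b* in both arms. The coded incidence is 1 − (1 − *b*)(1 − *d*), so the arm difference is (1 − *b*) × 20 points. Power uses the two-sided 5% normal approximation for two proportions, at the planned 75 per arm and at 25 per arm (the SAP 10.1 model indexes 51 patients; 51/2 = 25.5).

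| *b* | Coded incidence | Difference | Power, 75/arm | Power, 25/arm |
|---|---|---|---|---|
| 0 | 20% v 40% | 20 | 76.7% | 33.5% |
| 0.3 | 44% v 58% | 14 | 40.2% | 16.4% |
| 0.5 | 60% v 70% | 10 | 24.8% | 11.0% |
| 0.7 | 76% v 82% | 6 | 14.4% | 7.5% |

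The safety tables are descriptive, so power here only measures how far the contrast fades. It shrinks but does not vanish.

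**The case against.** The strongest reply is that nothing forces an event into Related. The lead-in requires clinical judgement about background illness, and the alternative-cause ground is an explicit exit. That stands, and it rules out a reading a reader might otherwise reach: that every adverse event must be coded related. It does not answer the overlap, because judgement is being exercised under two definitions that can both be true.

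A reader might also infer that the trial cannot tell whether adding pirfenidone causes limiting toxicity. The documents do not support this. Mycophenolate is given in both arms, and pirfenidone or placebo is randomised and double-blind. SAP section 11 tabulates by arm all TEAEs, all serious TEAEs, events of special interest, discontinuations due to adverse events and treatment failures. Endpoint 10a, time to stopping active drug for any reason, does not use relatedness.

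A third inference is that the same coding drives dose changes and unanticipated-problem reporting. The dose rules in Protocol 6.1.5 use other wording and already ask by drug ("Any adverse event felt by the investigator to be possibly or probably related to the administration of MMF"; "Any adverse event felt by the investigator to be possibly or probably related to the administration of PFD/Plac"). Section 8.3.3 uses its own two-level term alongside further criteria such as unexpectedness. Neither cites 8.2.2.

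Lastly, 8.2.2 speaks of one study agent, which might suggest that attribution is pooled over the two drugs. Protocol 8.3.1 refers to study drugs in the plural, and the adverse event form is not among the documents, so whether it holds one attribution or two is unknown.

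**Conclusion.** The concern holds for the two definitions and for the counts built on them: SAP endpoint 10b and safety items d and f. Those counts are assessor-dependent and can drift towards the all-TEAE counts. For serious events the committee limits variation between sites, but it applies the same text.

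The size is uncertain. In the earlier SSc-ILD trial the patient-level shift is at most 5 or 18 of 63, depending on how possibly related is treated. Endpoint 10b is split by organ class, where the shift could differ and the documents give no figure. The conclusion assumes that the TEAE window counts as a temporal relationship; the dilution table also rests on its assumed incidences.

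The primary endpoint, endpoint 10a and the randomised comparison of all TEAEs and serious events are unaffected and still estimate the effect of adding pirfenidone. This is a flaw in a secondary safety measure, worth correcting because the correction is short.

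**What to change.** **Protocol 8.2.2 and SAP 11.5.2.** Define Related as a reasonable possibility that the study agent caused the event. Compatible timing and known occurrence with the agent become supporting evidence, neither sufficient alone; removing only the timing ground would leave infections or diarrhea, both known with mycophenolate, automatically related in either arm. Define Not Related as the complement: no reasonable possibility, for example because the timing is incompatible or another cause accounts for the event. Exactly one category then applies. The committee in 8.5.1 inherits the change by reference. Leave the reporting wording in 8.3.3 as it is.

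**SAP.** Name the by-arm comparison of all TEAEs and serious events, together with endpoint 10a, as the main tolerability evidence. Label endpoint 10b and items d and f as investigator-judged. If the adverse event form already records attribution to mycophenolate and to pirfenidone/placebo separately, tabulate the two separately.

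**Cost.** A few sentences in each document and a short re-briefing of site and committee assessors; fewer events will count as related. SAP section 14 says enrollment stopped early. For data already collected, only the SAP statement and labelling apply unless events are re-reviewed, which is a much larger task.
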